5.8.2.2. Laboratory read-outs

In case of insufficient blood sample volume to perform all assays, the samples will be analyzed according to priority ranking provided in [Table 11](#), [Table 12](#) and [Table 13](#).

Table 11 Laboratory read-outs at each time point, and priority ranking for scheduled visits (Amended 16 October 2017)

SCHEDULED VISITS								
Blood sampling time point		No. Subjects (anticipated)	Subset*	Possible assays	Serum aliquot volume	Aliquot priority rank	Test priority rank	Aliquot number
Type of contact/ Amount of whole blood	Sampling time point							
Scheduled Visit 1 whole blood 5 mL	(Day 0)	3600 (1800 from wave 1 & 2***)	-	Dengue IgG ELISA**	250 µL	1	1	1
			yes	Dengue virus 1-4 neutralizing antibodies	1 mL	2	1	2
				YF neutralization			4	
				Zika neutralization			3	
				Zika serology (IgG) #			2	
			yes	Chikungunya serology (IgG) #	2			
yes	Chikungunya neutralization	remaining volume	3	1	3			
Scheduled Visit 2 5 mL whole blood	Visit 1+ 6 months for subject enrolled in Study Year 1; Visit 1+ 12 months for subject enrolled in beginning of Study Year 2, 3 or 4)	3190 (1660 from wave 1 and 1530 from wave 2)	yes	Dengue IgG ELISA** (only for subjects IgG negative at the previous visit)	250 µL	1	1	1
			yes	Dengue virus 1-4 neutralizing antibodies	1 mL	2	1	2
				YF neutralization			4	
				Zika neutralization			3	
				Zika serology (IgG) #			2	
			yes	Chikungunya serology (IgG) #	2			
yes	Chikungunya neutralization	remaining volume	3	1	3			

CONFIDENTIAL

116606 (EPI-DENGUE-006 BOD BR)
Protocol Amendment 4 Final

SCHEDULED VISITS								
Blood sampling time point		No. Subjects (anticipated)	Subset*	Possible assays	Serum aliquot volume	Aliquot priority rank	Test priority rank	Aliquot number
Type of contact/ Amount of whole blood	Sampling time point							
Scheduled Visit 3 5 mL whole blood	(Visit 2+ 6 months for subject enrolled in Study Year 1; Visit 2+12 months for subject enrolled in beginning of Study Year 2 or 3)	3030 (1530 from wave 1 and 1500 from wave 2)	yes	Dengue IgG ELISA** (only for subjects IgG negative at the previous visit)	250 µL	1	1	1
			yes	Dengue virus 1-4 neutralizing antibodies	1 mL	2	1	2
				YF neutralization			4	
				Zika neutralization			3	
				Zika serology (IgG) #				
			Chikungunya serology (IgG) #	2				
yes	Chikungunya neutralization	remaining volume	3	1	3			

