3.2. Secondary objectives

- To estimate the serotype-specific incidence of virologically-confirmed symptomatic dengue infection in the study population overall and by season.
- To estimate the incidence of symptomatic dengue infection (including laboratory-confirmed and probable cases) in the study population by study site, gender, age-group, previous dengue exposure (primary or secondary), overall and by season.
- To estimate the prevalence of previous dengue infection (dengue seroprevalence) in the study population overall and by study site, gender and age-group at enrolment.
- To estimate the incidence of primary inapparent dengue infection, in the study population overall and by study site, gender age-group and by season.
- To describe symptoms and spectrum of dengue disease in the study population.

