7.2. Analysis of primary and secondary endpoints

7.2.1. Analysis as planned per protocol

The following analyses will be performed overall and by DENV type, study site, gender and age-group previous dengue exposure (Yes = DENV IgG antibodies at previous visit and No = no DENV IgG antibodies at previous visit):

- Incidence rate of *laboratory-confirmed symptomatic dengue infection* with 95% CI for each season separately: the numerator will be the number of subjects with lab-confirmed symptomatic dengue infection during the season (between the visits scheduled before and after the season). The denominator will be the total person-years at risk, i.e. from the visit scheduled before the season until the first RT-qPCR confirmed symptomatic dengue infection during the season, the next scheduled visit or the subject's withdrawal, whichever comes first.

- Incidence rate of *laboratory-confirmed symptomatic dengue infection* with 95% CI all seasons combined: the numerator will be the number of subjects with lab-confirmed symptomatic dengue infection during the study period. The denominator will be the total person-years at risk, i.e. from enrolment until the first RT-qPCR confirmed symptomatic dengue infection, the end of the study or the subject's withdrawal, whichever comes first.

The following analyses will be performed by study site, gender and age-group previous dengue exposure (primary or secondary):

- Incidence rate of *laboratory confirmed or probable symptomatic dengue infections* with 95% CI for each season separately and overall. The numerator will be the number of subjects with symptomatic dengue infection (including laboratory-confirmed and probable cases) during the period. The denominator will be the total person-years at risk.
- Incidence rate of *probable symptomatic dengue infection* with 95% CI for each season separately and overall. The numerator will be the number of subjects with probable symptomatic dengue infection. The denominator will be the total person-years at risk.

The following analyses will be performed by study site, gender and age-group:

- The proportion of subjects with *primary inapparent dengue infection* at each subsequent scheduled visit (not at enrolment) with 95% CI will be calculated as the number of dengue IgG positive cases and at the visit divided by the total number of subjects IgG negative at the previous visit.

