- The proportion of subjects with *secondary symptomatic dengue infection (probable or confirmed)* at each subsequent scheduled visit (not at enrolment) with 95% CI will be calculated as the number of subjects with secondary symptomatic infection since the previous visit divided by the total number of IgG positive subjects at the previous visit.
- The (crude) *seroprevalence of dengue infection* will be calculated at enrolment and at each scheduled visit as a proportion (i.e., the number of dengue IgG positive subjects tested positive at this visit or known to be positive from previous visits divided by the total number of subjects for whom dengue IgG serostatus is known).

Endpoint numerators and denominators are described in [Table 1](#) below:

Table 1 Numerators and Denominators within each strata (DENV type, study site, gender and age-group and previous dengue exposure (primary or secondary))

Analysis	Numerator	Denominator
Incidence rate of laboratory confirmed symptomatic infection by year	All confirmed acute cases during the season (between the visits scheduled before and after the season)	Total person-years at risk, i.e. from the visit scheduled before the season until the first RT-qPCR confirmed symptomatic dengue infection during the season, the next scheduled visit or withdrawal, whichever comes first.
Incidence rate of laboratory-confirmed symptomatic dengue infection for all seasons combined	All confirmed acute cases during the study period	Total person-years at risk, i.e. from enrolment until the first RT-qPCR confirmed symptomatic dengue infection, the end of the study or withdrawal, whichever comes first.
Incidence rate of laboratory confirmed or probable symptomatic dengue infections	All symptomatic dengue infections (including laboratory-confirmed and probable cases) during the period.	Total person-years at risk*.
Incidence rate of probable symptomatic dengue infection	All probable symptomatic dengue infection	Total person-years at risk*.
Proportion of subjects with primary inapparent dengue infection	All dengue IgG positive cases at the considered visit	Total number of IgG negative subjects at the previous visit
Proportion of subjects with secondary symptomatic dengue infection	All symptomatic infection since the previous visit	Total number of IgG positive subjects at the previous visit
Seroprevalence of dengue infection	All dengue IgG positive cases	Total number of subjects tested or previously positive

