7.2.2. Additional considerations

7.2.2.1. Incidence rate

In light of the low number of dengue episodes, the large number of positive anti-dengue IgG at visit 1 and the number of dengue cases reported outside the season,

1. The analyses of PCR confirmed cases (only 10 cases) and the analyses of secondary dengue infections were removed.
2. The analyses by seroprevalence at each visit were removed,
3. The analyses by season were removed. Only the analyses by calendar year are to be conducted

- 4. Subjects without seroprevalence status at visit 1 were removed from the ATP cohort because serological status of symptomatic/inapparent dengue infections cannot be assessed properly for such subjects
- 5. Planned analyses of medical and vaccination history were removed.
- 6. The statistical method was updated to ignore the household cluster effect and to provide incidence rate with confidence interval in absence of dengue episodes in a calendar year for a study site .

Regarding the last point, the expected annual incidence rate for a cohort of subjects followed over a full calendar will be computed using a log-linear model with the number of dengue events (all cases) as depend variable and the total number of subject-month as offset. The model will include the study site, year and month as independent categorical fixed effects (see below).

The expected annual incidence rate in a study site for each year will be estimated as the average of incidence rate over months

```

proc genmod ;
  class center month year;
  model evt= center year month /
    dist=poisson link=log offset=ln TYPE3;

  ods output Estimates=estimc;
  estimate 'center PPD 2014' intercept 12 center 12 0 0 0 0
    year 12 0 0 0 0
    Month 1 1 1 1 1 1 1 1 1 1 1;
  estimate 'center PPD 2014' intercept 12 center 0 12 0 0 0
    year 12 0 0 0 0
    Month 1 1 1 1 1 1 1 1 1 1 1;
  estimate 'center PPD 2014' intercept 12 center 0 0 12 0 0
    year 12 0 0 0 0
    Month 1 1 1 1 1 1 1 1 1 1 1;
  estimate 'center PPD 2014' intercept 12 center 0 0 0 12 0
    year 12 0 0 0 0
    Month 1 1 1 1 1 1 1 1 1 1 1;
  estimate 'center PPD 2014' intercept 12 center 0 0 0 0 12
    year 12 0 0 0 0
    Month 1 1 1 1 1 1 1 1 1 1 1;
  estimate 'overall 2014' intercept 12 center 2.4 2.4 2.4 2.4 2.4
    y 12 0 0 0 0
    Month 1 1 1 1 1 1 1 1 1 1 1;
  estimate 'center PPD 2015' intercept 12 center 12 0 0 0 0
    year 0 12 0 0 0
    Month 1 1 1 1 1 1 1 1 1 1 1;
  estimate 'center PPD 2015' intercept 12 center 0 12 0 0 0

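### Primary inapparent infection is kept as a proportion per visit number, so at Visits 2 and 3 it pools 6-month with 12-month intervals and estimates neither risk

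*SAP*

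**What the plan says.** SAP Amendment 1, section 3.2, sets the secondary objective: "To estimate the incidence of primary inapparent dengue infection, in the study population overall and by study site", and also by gender, age group and season.

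The estimator is in section 7.2.1. The proportion is given "at each subsequent scheduled visit (not at enrolment"; IgG positives at the visit are "divided by the total number of subjects IgG negative at the previous visit". Table 1 repeats the denominator: "Total number of IgG negative subjects at the previous visit". The breakdown is introduced by "The following analyses will be performed by study site, gender and age-group". This row has no person-time and no stratum for cohort or interval length, whereas the symptomatic incidence rows of the same table use person-years. Protocol section 8.5.2 and Table 16 read the same way.

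Protocol Table 11 (section 5.8.2.2) places Visit 2 at "Visit 1+ 6 months for subject enrolled in Study Year 1; Visit 1+ 12 months for subject enrolled in beginning of Study Year 2"; those who join in later years also have the yearly step. Visit 3 has the same split, 6 or 12 months after Visit 2. Protocol Tables 5 and 6 and section 5.5.3 agree.

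SAP section 7.2.2.1 lists the changes made in Amendment 1. Item 3 says "The analyses by season were removed" and that calendar-year analyses alone will be done. No item names the inapparent proportion.

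**The concern.** A proportion among subjects negative at the last visit is a risk over whatever time separates the two samples. If one visit number closes a 6-month interval for some subjects and a 12-month interval for others, the pooled figure depends on the cohort mix as well as on transmission. A row with more expansion subjects then shows more seroconversion at an identical hazard. The Visit 2 and Visit 3 figures could not be set against each other, against later visits or against another study's annual risk, and the incidence named in the objective could not be read from them.

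**Working it through.** **Which cells are mixed.** The SAP section 7 table of sites and visits gives:

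| Site and cohort | Visits | Visit 1–2 and 2–3 intervals |
|---|---|---|
| Rio, Manaus, Salvador, initial | up to 6, 6, 5 | 6 months |
| Rio, replacement | 1 to 4 | 12 months |
| Manaus, replacement | 1 to 2 | 12 months |
| Natal, expansion | 1 to 3 | 12 months |
| Campinas, expansion | 1 to 2 | 12 months |

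Within a site, the mixture occurs at Rio (Visits 2 and 3) and Manaus (Visit 2). Gender and age rows mix at Visits 2 and 3. From Visit 4 every interval is about 12 months.

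**Reproducing the plan's own counts.** Table 11 anticipates 3190 subjects at Visit 2: 1660 from wave 1 and 1530 from wave 2. Protocol section 8.2.1 gives annual drop-out of 15 to 20%. At 15%:

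- wave 1 after 6 months: 1800 × 0.85^0.5 = 1659.5
- wave 2 after 12 months: 1800 × 0.85 = 1530.0
- total: 3189.5, against 3190

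At 20% the values are 1610 and 1440 and do not match. So Table 11 itself places 6 months behind Visit 2 for one wave and 12 for the other.

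**Five-site weights.** Campo Grande never enrolled (SAP section 2.1). Two expansion sites at planned size give 2 × 600 × 0.85 = 1020, so the Visit 2 mix is about 1660 : 1020, with 1020/2680 = 38% on a 12-month interval. Replacement numbers are not given and are left out. At Visit 3 the 12-month share should be smaller, because Campinas ended at Visit 2.

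**Effect on the pooled proportion.** Assume a 12-month risk p12 among IgG negatives and a constant hazard λ = −ln(1 − p12). Then p6 = 1 − exp(−λ/2), and pooled = (1660·p6 + 1020·p12)/2680.

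| Assumed p12 | p6 | Pooled at Visit 2 | λ per person-year, both cohorts |
|---|---|---|---|
| 2% | 1.0% | 1.4% | 0.020 |
| 5% | 2.5% | 3.5% | 0.051 |
| 10% | 5.1% | 7.0% | 0.105 |
| 20% | 10.6% | 14.2% | 0.223 |

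The last column is what a person-time rate would return in either cohort.

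**Effect on the age rows (p12 = 10%).** The Amendment 3 rationale in Protocol Appendix C gives 19% children and 28.8% older adults in the first two initial sites. The expansion limits are at least 30% under 18 and at most 20% aged 50 or older; the limits themselves are used here.

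- Under 18: 1660 × 0.19 = 315.4 and 1020 × 0.30 = 306; 12-month share 49%; pooled 7.5%.
- 50 or older: 1660 × 0.288 = 478.1 and 1020 × 0.20 = 204; 12-month share 30%; pooled 6.6%.
- Ratio, with no true age difference: 0.0753/0.0659 = 1.14 (1.136 to 1.148 over p12 from 20% down to 2%).

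**Season.** SAP section 2.4 puts the season at 1 January to 30 June at every site. If all risk fell there, a 6-month interval could hold none or all of the yearly risk. At p12 = 10%, pooled Visit 2 then runs from 1020 × 0.10/2680 = 3.8% to 10%.

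**The case against.** Section 7.2.1 is headed as the analysis planned per protocol, and section 10 places all changes in the additional-consideration sections. The same block still lists season, secondary-infection and per-visit seroprevalence analyses, which section 7.2.2 appears to remove, so its wording alone does not prove that a per-visit table will be produced. Section 7.2.2.1 also contains a person-time method: a log-linear model with subject-months as offset, by site and year, and exact Poisson limits for gender and age. Its event count is described as covering all cases, item 4 mentions inapparent infections, and section 7.3.2 lists inapparent as a laboratory category. On that view the remedy is a clarifying line for a secondary endpoint in a purely descriptive study.

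Part of this stands: the text does not settle which method applies, and the table shells are in a separate document. But no listed change names this proportion, so under section 10 it remains in force. A model by month needs a month for each event; a seroconversion between two samples has none, and sections 11.3.1 and 11.3.3 give no rule. The superseded June 2019 SAP had a per-season estimator with at-risk rules, which Amendment 1 does not carry over. If removal was intended, the objective has no estimator. Each reading needs a correction.

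Four stronger readings are not supported:

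- That visit number is the only time index left in the plan. Item 3 keeps calendar year; what is missing is the link from this proportion to it.
- That the roughly twofold gap between 6- and 12-month risks carries into the gender or age rows. It compares unmixed cohorts. Gender comparisons are unbiased if the gender mix is equal across cohorts, and the age ratio is about 1.14.
- That the intervals mix about evenly. That is the six-site plan.
- That every site row is affected. Salvador, Natal and Campinas each have one schedule.

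**Conclusion.** The point holds for Visits 2 and 3. Followed as written, the plan gives gender and age figures, plus Rio at both visits and Manaus at Visit 2, that are neither a 6-month nor a 12-month risk. It also leaves initial and expansion sites non-comparable at the same visit number. At an assumed 12-month risk of 10%, the pooled Visit 2 value is about 7.0%, between 5.1% and 10%.

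The size rests on an assumed risk (2 to 20% shown), a constant hazard and planned attendance as weights; the share IgG negative by cohort and age is not given. The age ratio of about 1.14 uses the mix of the first two initial sites. Salvador applied the age targets at enrolment (SAP section 2.2.4), so the distortion could be smaller. Seasonality could make the gap between the two intervals smaller or larger than the constant-hazard figures.

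**What to change.** In section 7.2.2, replace the per-visit proportion by inapparent seroconversions per 1000 person-years between consecutive sampling dates among IgG-negative subjects, overall and by site, gender, age group and calendar year. A complementary log-log model with log interval length as offset is an alternative. State how a seroconversion is dated (midpoint, or interval-censored), which also settles how an interval spanning two calendar years is assigned.

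Person-time alone does not remove seasonality, so add a full-year check that pairs Visit 1 with Visit 3 in the initial cohort. Show per-visit proportions only within cohort type.

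Cheap improvement: one changed table and a short SAP paragraph, using sampling dates already held. The downside is that infection time within the interval is unknown, so the rate depends on the dating convention chosen.

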8.2. Sample size consideration

8.2.1. Assumptions:

A target to obtain at least 500 subjects/site still active at the end of the first year of the study *is planned*. *Since* subjects might leave the study due to a variety of reasons, e.g. moving away geographically, sample size is increased to allow for this. On the basis of

an annual drop-out rate between 15 and 20%, approximately 600 subjects/site will be enrolled at the beginning of this study. The recruitment will be cluster sampling, i.e. the unit of sampling will be the households. Different areas where the FHP has been fully implemented or where access to the community is already established by a government program will be first selected, followed by a selection of households in the respective areas. All subjects in each household will be invited for recruitment to the study.

New sites will start enrolling subjects preferably during study Year 2. The target is to enrol approximately 600 subjects per additional site. Replacement subjects may be recruited in order to maintain at least 500 subjects/site still active at the beginning of the next dengue season.

In order to better represent the Brazilian population distribution, subjects enrolled in the expansion cohort should be composed of at least 30% of subjects younger than 18 years old and should not exceed 20% of adults 50 years or older. Subjects enrolled as replacement subjects for the initial and expansion cohort will be recruited to approach as much as possible a minimal representation of 30% of subjects younger than 18 years old and a maximal representation of 20% for adults 50 years or older.

The total study duration per site will last approximately 4 years for the initial cohort and approximately 3 years for the expansion cohort, and new subjects will be enrolled if the number of subjects still active in the study is below 500/site after year 1 and at the beginning of each additional study year/season.

Between 2007 and 2010, the average incidence of reported dengue cases in the Brazilian population was about 0.3% per year (or 0.003 cases per person per year). Assuming an underreporting factor of 3 (Brazil MoH, 2011) the average incidence of dengue is expected to be about 1% per year (or 0.01 cases per person per year).

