8.5.2. Analysis of primary and secondary endpoints

The following analyses will be performed overall and by DENV type, study site, gender and age-group previous dengue exposure (Yes = DENV IgG antibodies at previous visit and No = no DENV IgG antibodies at previous visit):

- Incidence rate of laboratory-confirmed symptomatic dengue infection with 95% CI for each season separately: the numerator will be the number of subjects with lab-confirmed symptomatic dengue infection during the season (between the visits scheduled before and after the season). The denominator will be the total person-years at risk, i.e. from the visit scheduled before the season until the first RT-qPCR confirmed symptomatic dengue infection during the season, the next scheduled visit or the subject's withdrawal, whichever comes first.
- Incidence rate of laboratory-confirmed symptomatic dengue infection with 95% CI all seasons combined: the numerator will be the number of subjects with lab-confirmed symptomatic dengue infection during the study period. The denominator will be the total person-years at risk, i.e. from enrolment until the first RT-qPCR confirmed symptomatic dengue infection, the end of the study or the subject's withdrawal, whichever comes first.

The following analyses will be performed by study site, gender and age-group previous dengue exposure (primary or secondary):

- Incidence rate of laboratory confirmed or probable symptomatic dengue infections with 95% CI for each season separately and overall. The numerator will be the number of subjects with symptomatic dengue infection (including laboratory-confirmed and probable cases) during the period. The denominator will be the total person-years at risk.
- Incidence rate of probable symptomatic dengue infection with 95% CI for each season separately and overall. The numerator will be the number of subjects with probable symptomatic dengue infection. The denominator will be the total person-years at risk.

The following analyses will be performed by study site, gender and age-group:

- The proportion of subjects with primary inapparent dengue infection at each subsequent scheduled visit (not at enrolment) with 95% CI will be calculated as the number of dengue IgG positive cases and at the visit divided by the total number of subjects IgG negative at the previous visit.

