11.2. Handling missing data

No data handling will be performed in case of missing data.

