The same analysis as describe above will also be generated by calendar year. For the analyses by calendar years the analysis periods will begin on 01-Jan and end on 31-Dec of the considered year.

In addition, the number of subjects at risk, the number of households with at least one event (i.e. laboratory-confirmed symptomatic dengue cases, laboratory-confirmed or probable symptomatic dengue cases, probable symptomatic dengue cases) and the total number of events reported during the follow-up period at risk will also be tabulated along with the incidence rates.

The following analyses will be performed by study site, gender and age category:

- The seroprevalence of dengue infection with 95% CI (refer to Section 12.1 for the methodology for computing 95%CI) will be calculated at Visit 1 (i.e. the number of subjects tested positive for dengue IgG at Visit 1 divided by the total number of subjects with dengue IgG results at Visit 1).
- The incidence proportion of subjects with primary inapparent dengue infection with 95% CI (refer to Section 12.1 for the methodology for computing 95%CI) will be estimated for each dengue season and overall. It will be estimated as the number of documented seroconversion (anti-dengue IgG antibodies) without clinical suspicion of dengue (identified during the time period in which seroconversion occurred, using the blood sampling dates) per total number of subjects at risk. The total number of subjects at risk will be calculated using dengue IgG results at the scheduled visits. Only subjects with available test results for two consecutive scheduled visits will be considered in the denominator by season. Only subjects negative for anti-dengue IgG antibodies at one visit will contribute for the following period of analysis. For overall seasons, only subjects with negative result for anti-dengue IgG antibodies at the scheduled visit planned before their first season follow-up and with either available anti-dengue IgG results for the scheduled visit planned after the last season or with positive result for anti-dengue IgG antibodies at any scheduled visits planned in between will be included in the denominator.

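### The inapparent-infection proportion does not follow its own definition in either the denominator or the numerator, and the net direction of the bias is unknown

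*SAP*

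**What the plan says.** SAP Amendment 1, section 7.2.1, defines the proportion at each scheduled visit after enrolment as "the number of dengue IgG positive cases and at the visit divided by the total number of subjects IgG negative at the previous visit". Table 1 in the same section gives the numerator as "All dengue IgG positive cases at the considered visit" and the denominator as "Total number of IgG negative subjects at the previous visit". The SAP takes this from Protocol 8.5.2, where the count is likewise "divided by the total number of subjects IgG negative at the previous visit", and from Protocol Table 16.

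Other parts of Amendment 1 bear on the formula:

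- Section 6.9 defines primary inapparent infection as IgG seroconversion between two successive scheduled-visit samples, with no clinical suspicion of dengue in that period.
- The seroprevalence bullet in section 7.2.1 is "divided by the total number of subjects for whom dengue IgG serostatus is known", so it does exclude subjects without a result.
- Section 5.1 admits subjects to the ATP cohort on a Visit 1 serostatus and does not ask for a later result.
- Section 11.2 says "No data handling will be performed in case of missing data".

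The superseded SAP of 14 June 2019, section 7.4, had the condition "Only subjects with available test results for two consecutive scheduled visits will be considered in the denominator by season", and counted only seroconversions without clinical suspicion. The interim-analysis SAP said the same. Amendment 1 carries forward neither rule in its formula. Its lists of changes (sections 1 and 7.2.2.1) do not mention dropping them.

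**The concern.** Two groups are misplaced if the formula is programmed as written.

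The first is seronegative subjects who left, moved, missed the visit or gave no sample. They cannot enter the numerator, but they remain in the denominator and so count as uninfected. This pulls the proportion down.

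The second is subjects who seroconverted and also had a suspected dengue episode in the interval. Section 6.9 does not call these inapparent, yet the numerator takes every IgG positive. This pushes the proportion up.

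The incidence of primary inapparent infection is a secondary objective, to be reported overall and by site, gender and age group (SAP 3.2). Interval length also differs by design. Initial sites have two 6-month intervals in their first year, while expansion sites have 12-month intervals (Protocol Tables 5 and 6). With a constant loss rate, the denominator error would therefore not be the same across the cohorts being compared.

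**Working it through.** **Inputs.** Protocol 8.2.1 plans for "an annual drop-out rate between 15 and 20" percent. Protocol Table 11 anticipates 1800 samples per wave at Visit 1. At Visit 2 it anticipates 1660 for wave 1 (6 months) and 1530 for wave 2 (12 months). At Visit 3 it anticipates 1530 for wave 1 (12 months). Protocol Table 15 gives 1661.3 person-years for 1800 subjects over one year.

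**Reproducing the plan's figures.** With constant 15% annual loss:

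- 6 months: 1800 × √0.85 = 1659.5 (stated 1660)
- 12 months: 1800 × 0.85 = 1530 (stated 1530)
- person-years: 1800 × 0.15 / (−ln 0.85) = 1661.3 (stated 1661.3)

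All three agree, so the planned untested share can be read from this model.

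**Untested share, u.**

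- 15% a year: 1 − √0.85 = 7.8% per 6 months; 15% per 12 months
- 20% a year: 1 − √0.80 = 10.6% per 6 months; 20% per 12 months

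The wave 2 step from 1530 at Visit 2 to 1500 at Visit 3 (2%) is left out. It is held up by the replacement floor and does not measure retesting.

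**Denominator alone.** If untested subjects have the same risk as tested ones, reported = true × (1 − u). The relative bias is −7.8% to −10.6% per 6-month interval and −15% to −20% per 12-month interval. For an assumed true 5%, the reported value is 4.5–4.6% at 6 months and 4.0–4.25% at 12 months.

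If risk in the untested is RR times that in the tested, reported/true = (1 − u) / [(1 − u) + u × RR]. At u = 15%:

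- RR = 0.5: 0.85 / 0.925, or −8.1%
- RR = 2: 0.85 / 1.15, or −26.1%

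**Both parts as written.** Let s be the share of tested seroconverters who had clinical suspicion of dengue. With equal risk, reported/true = (1 − u) / (1 − s). The documents give no value for s, so 0–30% is assumed.

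| u | s = 0 | s = 10% | s = 20% | s = 30% |
|---|---|---|---|---|
| 7.8% | −7.8% | +2.4% | +15.3% | +31.7% |
| 15% | −15.0% | −5.6% | +6.2% | +21.4% |
| 20% | −20.0% | −11.1% | 0.0% | +14.3% |

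The errors cancel at s = u, and the sign turns positive when s exceeds u.

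**Correcting the denominator only.** The ratio becomes 1 / (1 − s). At s = 20% that is +25%, against +6.2% for the uncorrected formula at u = 15%. A half-correction can make the estimate worse.

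**The case against.** **The text may not tell anyone to count untested subjects as negative.** Section 7 of the SAP says that, from Visit 2, an IgG result will be available for subjects negative at the visit before. Section 11.2 reads most naturally as a statement that nothing will be imputed, and treating an untested subject as uninfected is in effect an imputation. This stands in part. A reader might infer that section 11.2 forbids a paired-result denominator, but it does not say so. It does not supply one either, and the neighbouring seroprevalence bullet shows that the condition is written out where it is meant.

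**The proportion may no longer be planned.** Section 7.2.1 repeats the protocol so closely that it still lists by-season analyses, which section 7.2.2.1 removes. That section also removes analyses by seroprevalence at each visit. However, the objective (3.2), the endpoint (4.2), the formula (7.2.1) and the inapparent category (7.3.2) all remain. The status needs to be stated, but the doubt does not dispose of the point.

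**The effect may be small for a descriptive secondary endpoint.** At an assumed 5%, the denominator error is 0.4–1.0 percentage points. With an assumed 100–600 seronegatives, the 95% half-width is 1.96 × √(0.05 × 0.95 / n), or 4.3 to 1.7 points before clustering. This is fair for a single site. But this error is systematic, so larger numbers or pooling would not remove it.

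**The loss rate is a planning figure for all subjects.** It is not observed missingness among IgG negatives. This stands.

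**Conclusion.** The formula in SAP Amendment 1, section 7.2.1 and Table 1 (and in Protocol 8.5.2 and Table 16) does not estimate what section 6.9 defines. The denominator, taken alone, biases the proportion low by the untested share: about 8–11% per 6-month interval and 15–20% per 12-month interval, relative to the true value. This rests on the planned 15–20% annual drop-out applying to seronegative subjects, and on untested subjects having the same risk as tested ones. The literal numerator biases it high by an unknown amount, so the net direction is unknown.

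Two stronger readings are tempting and are not supported. A reader might infer that the reported proportion must be 8–20% too low. That holds only if no seroconverter had a suspected episode, and the documents do not show this. A reader might also infer that the bias is known to differ between sites and age groups. The documents give no drop-out by site or age, and only the difference in interval length is visible.

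**What to change.** In SAP section 7.2.1 and Table 1, with matching wording in Protocol 8.5.2 and Table 16, change both parts in one edit:

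- **Numerator:** subjects who seroconverted for IgG at the considered visit with no clinical suspicion of dengue in that interval, as in section 6.9.
- **Denominator:** subjects who were IgG negative at the preceding scheduled visit and have an IgG result at the considered visit. This restores the paired-result condition of the June 2019 SAP.

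Tabulate the number not retested by site beside the estimate. State in section 7.2.2 whether this per-visit proportion is retained after the removals listed there.

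The cost is a few lines of text, one extra tabulation, a smaller denominator and a slightly wider interval. No new data are needed. The paired denominator removes the error only if loss is unrelated to infection. At u = 15% and RR = 0.5 or 2, it would still be off by +8.1% (1 / 0.925) or −13.0% (1 / 1.15), which is why the count of those not retested should be shown.
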